The diagnosis of CPF is made clinically based on history and physical exam [6]. Confirmation with diagnostic imaging may be necessary when the symptoms are atypical or are refractory to treatment. MRI is a useful diagnostic tool to evaluate for plantar fascia thickening and edema in and around the fascia, both of which are consistent with the diagnosis of CPF. In addition, many physicians use MRI to exclude other causes of plantar heel pain [7]. Ultrasound can also be used to quantify the thickness of the plantar fascia. Multiple studies have shown that patients with CPF have increased thickness of the fascia compared to asymptomatic individuals [8-12]. Mean thickness in these studies for subjects with CPF range from 4.8-6.5 mm as opposed to 2.3-4.0 mm for subjects without the disease [8-13]. One of the studies showed that the thickness was increased in medial, central and lateral bands of plantar fascia uniformly along with 68% of patients with CPF reporting central band tenderness as opposed to 26% having lateral band tenderness [12]. In addition to the evidence of inflammation [9], the presence of a hyperechoic lesion in the plantar fascia was noted in 68% [10] to 84% [8] of patients with

CPF. Diagnostic ultrasound has also been used to quantify the effectiveness of treatments such as extra-corporeal shock wave therapy, NSAIDs and Botox injections for subjects with CPF [11, 13].

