#### Outcome measures

Subjects will complete subject reported outcome instruments, and will undergo a focused physical examination and diagnostic ultrasound at 0, 4, 8, 12 weeks. At 2, and 24 weeks a phone survey will be administered by the Clinical Coordinator using the same subject report outcome questionnaires. Adverse events, if any, and treatment tolerability will be recorded at each visit and 2-3 days after each treatment.

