#### Aim 2: Assessment of Perifascial Hypoechoic Lesions

Diagnostic ultrasound imaging will be performed with an FDA 510(k) cleared ultrasound scanner (Spark® System, Ardent Sound, Inc. – Mesa, AZ, see Appendix 5) using a coupling gel (Polysonic® Parker Laboratories, Inc., Fairfield, NJ, see Appendix 6) by a trained sonographer or physician. The subject will positioned prone on an exam table with the feet over the edge of the table. The plantar fascia of the affected and contralateral feet will be imaged. The thickness and depth of the fascia as well as the size and location of any hypoechoic lesion(s), when present, will be recorded using both long and short axis imaging. Change in the volume of hypoechoic plantar fascial lesions relative to the baseline measurement will be calculated.

[figure not shown]
[figure not shown]

Figure 4: representative long and short axis ultrasound images

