TITLE: Preliminary Protocol for Intense Therapeutic Ultrasound for the Treatment of Chronic Plantar Fasciitis

PROTOCOL NO.: WIRB® Protocol #20160753

DATE: May 26, 2016

SPONSOR: Guided Therapy Systems

[name]

[name]

INVESTIGATOR: [name]

[name]

[name]

Statistical Approach:

- Pain Reduction:

Pain level at the plantar fascia was self-reported by subjects at pre-treatment (used as baseline measurement) and again at each follow-up - 4, 8, 12, and 26 weeks - after initial treatment. The pain scale subjects used to identify their level of pain was a 10-point pain scale range, where 0 = no pain, 1 = slight pain through 10 which equates to the patient's worst imaginable pain. The goal for all subjects in the treatment group was to reduce pain by at least 25%. For patients reporting an initial (baseline) score ranging 6-10, this reflects a VAS pain score reduction  $\geq$  a 2 point drop; for initial scores ranging 2-5, this reflects a VAS pain score reduction  $\geq$  a 1 point drop. Pain scores reported at follow-up timepoints were compared to baseline score for each subject to determine if the goal was met by dividing the difference in the follow-up and baseline pain score by the baseline pain score. The percentage of subjects that met the pain reduction goal was calculated at each timepoint for both control and treatment groups by dividing the number of subjects that achieved the pain reduction goal at each timepoint by the total number of patients that gave a pain score for that time point.

- Plantar Fascia Hypoechoic Lesion Size:

A large proportion of patients suffering from chronic plantar fasciitis present with hypoechoic lesions in or around the proximal plantar fascia, as viewed by diagnostic ultrasound imaging.

Hypoechoic lesions were imaged and volumes were calculated at the baseline visit and each follow-up visit by measuring the inferior-to-superior and posterior-to-anterior radii in the long axis and the medial-to-lateral radius of the transverse axis and applying the following formula for the volume of an ellipse:

$$\text{Volume} = (4/3)\pi \cdot r_1 \cdot r_2 \cdot r_3$$

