With  $r_1$ ,  $r_2$ , and  $r_3$  representing the three radii detailed above. Changes to lesion volumes were recorded at each follow-up timepoint and compared to baseline by dividing the volume of the lesion at that timepoint with the volume of the same lesion at pre-treatment baseline.

- Foot Function Index Score Reduction:

In addition to the 10-point VAS pain scale, patients self-reported answers to questions from the Foot Function Index (FFI) pain subscale questionnaire, which has been standardized in a number of PF-focused publications . Scores range from 0-90, with 0 indicating no pain and 90 indicating the worst pain imaginable in a variety of daily activities involving use of the plantar fascia. Self-reported scores were taken at baseline and each follow-up timepoint. The average score for each timepoint were calculated, and follow-up averages were compared to baseline to calculate the percentage reduction in score.

- Hypoechoic Lesion Size – Pain/Function Correlation:

To determine the strength of a linear relationship between pain/function score reduction and lesion size reduction, linear regression was performed. Patient data related to pain/function score reduction at each follow-up timepoint compared to baseline were matched with corresponding data related to lesion size reduction. The average pain reduction percentage for each follow-up timepoint was paired with the average lesion size reduction percentage for the same follow-up timepoint to generate a data point for linear regression and the Pearson-correlation coefficient ( $r$ ) calculation.  $R$ -values found between 0.6 and 0.8 were considered strong and  $>0.8$  were considered very strong.

- Statistical Calculations

Student T-tests were utilized to determine statistically significant differences between baseline and subsequent follow-up measurements for self-reported and lesion size measurements. All error bars displayed in graphs are standard error. The level of significance ( $\alpha$ ) was set to 0.05.

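### The pain–lesion correlation is computed on three or four visit averages, so an r labelled strong or very strong need not reflect any link within patients

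*SAP*

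**What the plan says.** The SAP section on the correlation between hypoechoic lesion size and pain/function sets out to measure how strong the linear relationship is between the two reductions. It begins at patient level: "Patient data related to pain/function score reduction at each follow-up timepoint compared to baseline were matched with corresponding data" on lesion size. The next sentence averages before anything is correlated: "The average pain reduction percentage for each follow-up timepoint was paired with the average lesion size reduction percentage for the same follow-up timepoint", and this is done "to generate a data point for linear regression and the Pearson-correlation coefficient". The unit entering r is therefore a visit, not a patient.

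On interpretation, R-"values found between 0.6 and 0.8 were considered strong", and those above 0.8 very strong. The section gives no number of points, confidence interval or test for r.

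The documents differ on how many visits supply a pair:

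- **Protocol, Outcome measures:** subjects "will undergo a focused physical examination and diagnostic ultrasound at 0, 4, 8, 12 weeks". Aim 2 follows lesions for 12 weeks, and the week 24 contact is by telephone.
- **SAP:** pain is listed at weeks 4, 8, 12 and 26, and "Hypoechoic lesions were imaged and volumes were calculated at the baseline visit and each follow-up visit".

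The SAP names control and treatment groups only for the pain-reduction goal. It does not say whether the correlation pools or separates them.

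**The concern.** There are two separate faults.

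**Too few points.** The number of points equals the number of imaged follow-up visits, however many patients are enrolled. With three or four points, a large r arises easily by chance, and the fixed cut-offs of 0.6 and 0.8 make no allowance for that.

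**Shared time course.** Averaging over patients removes the between-patient variation that would show whether those whose lesions shrink are those whose pain falls. What remains is two average time courses. If both rise over the visits they correlate, whatever happens within patients.

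The protocol's hypothesis (Purpose of Study) covers both pain relief and a decrease in perifascial lesions. A very strong r would readily be read as evidence that the two go together, and this statistic cannot support that reading.

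**Working it through.** The documents give no value of r, so there is no figure to reproduce.

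**Step 1. Number of points.** Imaging at weeks 0, 4, 8 and 12 leaves three follow-up pairs, so r has 3 − 2 = 1 degree of freedom. If week 26 were imaged there would be four. If control and treatment averages were plotted as separate points there would be 3 × 2 = 6 or 4 × 2 = 8.

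**Step 2. Chance alone.** For unrelated normal data, t = r√((n − 2)/(1 − r²)) has n − 2 degrees of freedom. With n = 3:

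- r = 0.6: t = 0.6 × √(1/0.64) = 0.75, so P(r > 0.6) = 0.295.
- r = 0.8: t = 0.8 × √(1/0.36) = 1.333, so P(r > 0.8) = 0.205.
- Two-sided 5% critical value: t = 12.706, so |r| = 12.706/√(12.706² + 1) = 0.997.

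| Points | P(r > 0.6) | P(r > 0.8) | Critical \|r\| |
|---|---|---|---|
| 3 | 0.295 | 0.205 | 0.997 |
| 4 | 0.200 | 0.100 | 0.950 |
| 6 | 0.104 | 0.028 | 0.811 |
| 8 | 0.058 | 0.009 | 0.707 |

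The SAP sets α = 0.05 without stating sidedness; two-sided is assumed here.

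**Step 3. Shared time trend.** This step needs inputs that the documents do not give, so all of the following are assumptions: mean percentage reductions by visit, SD 40, within-subject correlation 0.5, and zero association between a patient's pain and that patient's lesion. The number analysed, 20 to 25, applies the 68% to 84% lesion prevalence in the protocol's Background (printed there as hyperechoic) to the maximum of 30 subjects: 0.68 × 30 = 20.4 and 0.84 × 30 = 25.2.

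| Assumed means (pain; lesion) | N | P(r > 0.6) | P(r > 0.8) |
|---|---|---|---|
| Steep: 20/40/55; 20/40/50 | 20 | 0.969 | 0.879 |
| Steep | 25 | 0.986 | 0.913 |
| Shallow: 30/40/45; 25/35/45 | 20 | 0.736 | 0.568 |
| Shallow | 25 | 0.784 | 0.621 |
| Shallow with a fourth visit (50; 50) | 25 | 0.834 | 0.594 |
| Early pain plateau, late lesion response: 40/45/45; 10/20/40 | 25 | 0.46 | 0.33 |
| Pain flat: 40/40/40; 25/35/45 | 25 | 0.291 | 0.205 |
| No trend in either | 25 | 0.298 | 0.206 |

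The no-trend row agrees with Step 2, so measuring the same patients repeatedly does not itself disturb the chance figures. Varying SD over 30–50 and within-subject correlation over 0.3–0.7 at N = 20 moves P(r > 0.8) to 0.70–0.99 (steep) and 0.41–0.81 (shallow).

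**Step 4. Association in the wrong direction.** With an assumed patient-level correlation of −0.3, r of the visit averages still exceeded 0.8 in 50% (N = 20) and 55% (N = 25) of trials with shallow trends, and in 83% and 87% with steep trends.

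**Step 5. Other assumed inputs.** With means of 25/45/60 for both measures, SD 25–45, N = 20 or 30 and no patient-level association, the median r of the averages was 0.96–0.99 while the median patient-level r was about 0.

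**The case against.** The strongest reply has four parts.

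1. **The SAP's own text points to four visits, not three.** At four points the chance of r above 0.8 halves to 0.10, and at six or eight separately plotted points it is rare (0.028 and 0.009). This stands as a limit on the chance argument, which is strong only at three or four points. It does not answer the time-trend argument: a fourth visit left P(r > 0.8) at 0.594 under shallow trends.
2. **The large simulated percentages rest on assumed means, SDs and correlations.** This also stands. The inflation depends on roughly parallel time courses, and it falls to 33% above 0.8 under an early pain plateau with a late lesion response, and to chance when pain is flat. But steady improvement in both measures is what the study hopes to see, and that is where the method misleads most.
3. **The analysis is exploratory.** It appears in no protocol aim and not in the protocol's statistical analysis section, and the SAP never explicitly claims a patient-level relationship. That limits the severity. It does not make the labels meaningful for the SAP's stated purpose.
4. **The SAP does match patient data.** True, but the averages, not the matched pairs, are what enter r.

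**Conclusion.** The concern holds and should be fixed. As written, the SAP can call a relationship very strong when there is none between patients, or when it runs the other way. On the protocol's schedule the chance of an r above 0.8 from unrelated averages is about one in five (one in ten with four points); this rests only on the number of points and normality. Under steady improvement in both measures it was 57–91% in the main simulations, which rests on the assumed trends, SD 40, within-subject correlation 0.5 and 20–25 subjects.

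The damage is confined to this exploratory analysis. The paired comparisons with baseline for the protocol's aims do not depend on it.

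**What to change.** **Change.** Use the matched patient-level pairs that the SAP already describes.

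- Restrict the analysis to subjects with a measurable baseline lesion. The protocol's Aim 2 has "size and location of any hypoechoic lesion(s), when present, will be recorded", and a percentage change is undefined without one.
- Fit a mixed model of each subject's pain (or FFI pain) change on the same subject's lesion-volume change at weeks 4, 8 and 12, with week as a fixed effect and subject as a random intercept. State whether the slope is meant to describe differences between patients, changes within them, or both.
- Report the slope, or a week-adjusted correlation, with its 95% CI and the number of subjects.
- Remove the 0.6 and 0.8 labels. If the visit averages are plotted, call them descriptive and state the number of points.

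The week adjustment is essential. Under steep trends with no patient-level association, false-positive rates at 5% for N = 20 and 25 were:

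| Method | Without week | With week |
|---|---|---|
| Repeated-measures correlation | 35%, 43% | 5%, 5% |
| Random-intercept model (400 trials each) | 27%, 31% | 5.8%, 3.3% |

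A simpler alternative is a patient-level correlation at one named visit with its CI. With 30 subjects, two-sided significance would need |r| ≥ 0.361.

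**Cost.** No new data are needed. The SAP is written in the past tense, so results may have to be rerun as well as the text revised. The estimate will probably be smaller and imprecise. For a week-adjusted correlation near zero with complete visits, the Fisher half-width is tanh(1.96/√(2N − 4)): 0.28 for N = 25 and 0.32 for N = 20. Subjects without a baseline lesion drop out of this analysis only.

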#### Statistical analysis

Data will be assessed for variance homogeneity and normality. FFI-P scores, PFCAT, FAAM scores before and after intervention will be compared using a paired t-test. Perifascial lesion volume is measured before and at each post treatment clinical visit using diagnostic ultrasound imaging, and paired t-tests will be utilized for comparison. For determination of statistical significance, a cutoff value of  $\alpha=0.05$  has been selected prior to start of data analysis.

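### The SAP's FFI percentage reduction compares visit averages without requiring the same subjects at both visits, so it can partly reflect who is missing

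*SAP*

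**What the plan says.** The SAP, under Foot Function Index Score Reduction, puts the FFI pain subscale on a 0 to 90 scale, averages it at baseline and at each follow-up, and states that "follow-up averages were compared to baseline to calculate the percentage reduction in score". It does not say which subjects enter the baseline average for a given follow-up.

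The SAP, under Pain Reduction, divides the number of responders at each timepoint by the number of patients who gave a pain score at that timepoint. The plan thus expects that number to vary between visits.

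On testing, the protocol (Statistical analysis) is explicit. For the questionnaires, "FFI-P scores, PFCAT, FAAM scores before and after intervention will be compared using a paired t-test"; for lesion volume, "paired t-tests will be utilized for comparison". The SAP (Statistical Calculations) says "Student T-tests were utilized to determine statistically significant differences between baseline and subsequent follow-up measurements" and adds "All error bars displayed in graphs are standard error", without naming the form of the t-test or the quantity whose standard error is shown.

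**The concern.** A before-after study without a concurrent comparison in its test rests entirely on change within subjects. A ratio of two visit averages equals the change in a fixed group only if the same people contribute to both. If the baseline average includes everyone enrolled and the follow-up average only those who answered, the percentage mixes two things: how much the remaining subjects changed, and how their baseline differed from that of the subjects who are missing. With at most 30 subjects (protocol, Selection of Subjects), a few absences can move the average visibly.

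There is also a problem of consistency. A paired t-test, as the protocol requires, uses only subjects with both measurements. A percentage built on all available scores could then sit beside a p-value that refers to a different set of subjects.

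**Working it through.** The plan gives no FFI mean, standard deviation, effect size, dropout rate or power, so there is no figure of its own to reproduce. The numbers below are illustrations; only the maximum of 30 subjects and the 0 to 90 scale come from the documents.

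**FFI percentage reduction**

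Let N be the number at baseline, m the number missing at a follow-up, B the mean baseline of those who stay, and B + d the mean baseline of those who are missing. Suppose that nobody's score changes.

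- Baseline average of all subjects = [(N − m)·B + m·(B + d)] / N
- Follow-up average of those who stay = B
- Apparent reduction = 1 − B / (baseline average of all subjects)

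Assumed: N = 30, m = 8, B = 50, d = 10.

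- Baseline average = (22 × 50 + 8 × 60) / 30 = 1580 / 30 = 52.67
- Apparent reduction = 1 − 50 / 52.67 = 5.1%
- In the 22 subjects with both scores: 1 − 50 / 50 = 0%, which is the true change

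Range over other assumptions, with B = 50 and no true change:

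| Missing of 30 | Mean baseline of the missing | Baseline average, all | Apparent change |
|---|---|---|---|
| 4 | 60 | 1540 / 30 = 51.33 | 2.6% reduction |
| 8 | 60 | 1580 / 30 = 52.67 | 5.1% reduction |
| 8 | 70 | 1660 / 30 = 55.33 | 9.6% reduction |
| 8 | 40 | 1420 / 30 = 47.33 | 5.6% increase |

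The artefact is zero if no one is missing or if the missing subjects have the same mean baseline as the rest.

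**Form of the t-test (conditional only)**

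If an independent-samples test were applied to these data, then with equal standard deviations and baseline-to-follow-up correlation ρ its standard error would exceed the paired one by the factor 1/√(1 − ρ). At ρ = 0.5 this is 1/√0.5 = 1.41.

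Assume 30 complete pairs, a mean change of 0.5 SD and two-sided α of 0.05. Paired power comes from the noncentral t distribution, and the unpaired results come from 100,000 simulated data sets.

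| ρ | Paired power | Unpaired power | Unpaired type I error |
|---|---|---|---|
| 0 | 0.47 | 0.48 | 0.051 |
| 0.3 | 0.61 | 0.47 | 0.020 |
| 0.5 | 0.75 | 0.47 | 0.007 |
| 0.7 | 0.93 | 0.47 | 0.001 |

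With positive correlation an unpaired test would be conservative. Only a negative correlation would inflate the error rate (0.074 at ρ = −0.2).

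**The case against.** A reader might infer more: that dropping the word paired, describing averages and plotting standard errors together amount to an unpaired analysis, with p-values and error bars that ignore the pairing. The text does not support this.

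- Student's t-test is a family name that includes the paired form. Nothing in the SAP says unpaired, two-sample or independent, and nothing revokes the protocol's paired test.
- The averages are described for the FFI percentage and for the correlation data points. The t-test sentence speaks of measurements.
- Elsewhere the SAP works within subject or lesion: "Pain scores reported at follow-up timepoints were compared to baseline score for each subject", and for lesions it describes "dividing the volume of the lesion at that timepoint with the volume of the same lesion at pre-treatment baseline".
- The standard errors are not said to be those of visit means. If they were, that would be an ordinary descriptive display, though not one from which to judge within-subject change.

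All of this stands, and it reduces the t-test and error-bar matter to missing detail.

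Against the FFI point it can be said that the percentage is descriptive, that the SAP does not state that all baseline scores are used, and that the dropout example is invented and could run either way. These are fair limits on its size and direction. They do not remove the gap: the rule as written permits unmatched averages, and the plan itself foresees different numbers by visit.

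**Conclusion.** The point holds for the FFI percentage reduction. As written, the rule can compare different sets of subjects and report a change due only to who is absent. The size cannot be known from the documents. It was 5.1% in the main example and between a 9.6% reduction and a 5.6% increase over the assumptions tried. The direction depends on whether the more or the less severely affected subjects are missing.

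The form of the t-test and the meaning of the standard error need clarifying, and no more than that. The contrast of 0.47 with 0.75 in power would arise only if the tests were unpaired, and only under the assumed 30 pairs, 0.5 SD change and correlation of 0.5.

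**What to change.** In the SAP's FFI section, state that each visit's percentage reduction is computed from subjects with both a baseline score and a score at that visit. Report the number of pairs, their baseline and follow-up means, and the mean within-subject change with its 95% CI.

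As a clarification in Statistical Calculations, repeat that the tests are paired t-tests, matching the protocol, and say whether each plotted standard error belongs to a visit mean or to a within-subject change.

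The cost is some SAP wording and a recalculation from data already collected. Baseline scores of subjects missing a visit drop out of that visit's comparison, so the reference mean may differ between visits. Matching removes the artefact of unequal groups. It does not remove bias if the subjects who stay respond differently from those who leave, and the report should say so.
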